**Response variables**

- Response variables will be summarized using frequency counts and percentages per visit or period as indicated in Table 11.
- An exact logistic regression model similar to the model described in Section 10.2 will be applied. No odds ratios will be calculated for the variables “Subjects meeting DOW at least twice per period” and “Subjects meeting DOW more than twice per period”.

**Cumulative distribution function**

- Change from reference visit will be summarized using frequency counts of levels of improvements/worsening,
- The Kolmogorov-Smirnov test will be used to test the equality of the two distribution functions.

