**Table 3: Assumptions for Power Analysis**

Treatment Sequence A	Probability of having a TIS $\geq 20$ points at Week 17	Probability of having a TIS $\geq 20$ points at Week 21	Probability of having a TIS $\geq 20$ points at Week 25
A	65%	90%, if TIS $\geq 20$ points at Week 17	90%, if TIS $\geq 20$ points at Week 21
		20%, if TIS $< 20$ points at Week 17, or withdraw, or receive oral rescue corticosteroid treatment before Week 17	20%, if TIS $< 20$ points at Week 21, or withdraw, or receive oral rescue corticosteroid treatment before Week 21
B	30%	90%, if TIS $\geq 20$ points at Week 17	90%, if TIS $\geq 20$ points at Week 21
		10%, if TIS $< 20$ points at Week 17, or withdraw, or receive oral rescue corticosteroid treatment before Week 17	10%, if TIS $< 20$ points at Week 21, or withdraw, or receive oral rescue corticosteroid treatment before Week 21

A Treatment sequence A = 0.5 g/kg IgPro20 for 24 weeks followed by 0.5 g/kg IgPro20 for 28 weeks; Treatment sequence B = placebo for 24 weeks followed by 0.5 g/kg IgPro20 for 28 weeks.

Simulation shows a total of 126 subjects (63 subjects per treatment sequence) will be required for a power of 90% in 1-sided Fisher's exact test at a significance level of 0.025. Fisher's exact test is used in the power simulation as a close approximation to the exact logistic regression model in the primary endpoint analysis.

For further details see [Appendix 14.1](#).

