## 8.2.19 EQ-5D-5L

The subject will select which best describes his own health state at the study visit in the following 5 dimensions: Mobility, Self-care, Usual Activities, Pain / discomfort, and Anxiety / depression. The subject will also select a point on a scale drawn like a thermometer to indicate how good or bad the health state is, with best state as '100' and worst state as '0'.

A unique health state is defined by combining 1 level from each of the 5 dimensions. A total of 3125 possible health states is defined in this way. Each state is referred to in terms of a 5 digit code. For example, state 11111 indicates no problems on any of the 5 dimensions, while state 12345 indicates no problems with mobility, slight problems with washing or dressing, moderate problems with doing usual activities, severe pain or discomfort and extreme anxiety or depression. EQ-5D-5L health states will be converted into a single index value. This index value will be derived using the EQ-5D-5L\_Crosswalk\_Index\_Value\_Calculator.v2.xls [[van Reenen, 2015](#)].

Index values are defined for several countries. Not all countries participating in this study are available in the Index Value Calculator. For this, the United Kingdom value set is used for all subjects, regardless whether their country is available in the calculator.

If one or more of the 5 dimensions are missing, the index value cannot be derived and is missing as well.

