## 10.5 Analysis of Secondary Efficacy Endpoint

All secondary efficacy analyses will be performed for the following periods and analysis sets:

- Week 1-25 by treatment sequence (mITT)
- Week 25-53 by treatment sequence (mITT-Ex)

Raw data and changes from the reference visit will be summarized at all visits as appropriate (Table 11). Comparison between treatment sequences will be performed using statistical models as described below. No imputation is planned for missing data in secondary endpoints. P-values from the statistical models are descriptive.

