**Table 11: Secondary Efficacy Endpoints - Variables**

Endpoint	Variable	Type of summary measure
TIS from Week 5 to Week 53	• TIS values	• continuous
	• Subjects achieving TIS $\geq 20$ points per visit • Subjects achieving TIS $\geq 40$ points per visit • Subjects achieving TIS $\geq 60$ points per visit • Subjects achieving TIS $\geq 20$ points at the end of Study Period 2	• response
	• Time to first achieving TIS $\geq 20$ points • Time to first achieving TIS $\geq 40$ points • Time to first achieving TIS $\geq 60$ points	• time to event
CDASI from Baseline to Week 53	• CDASI total activity score  Note: For Study Period 2 changes from baseline will also be calculated	• continuous
CSMs (except muscle enzymes) from Baseline to Week 53	• Physician Global Disease Activity • Patient Global Activity • MMT-8 • HAQ-DI • Extramuscular global activity	• continuous

Endpoint	Variable	Type of summary measure
	Note: For Study Period 2 changes from baseline will also be calculated	
DOW from Baseline to Week 53	
 
Subjects meeting DOW at least once per period
 
Subjects meeting DOW at least twice per period
 
Subjects meeting DOW more than twice per period
 
	• response
	• Time to meet DOW for the first time	• time to event
	• Subjects meeting DOW followed by oral rescue corticosteroid treatment per period	• response
Oral rescue corticosteroid treatment (from Baseline to Week 25)	
 
Subjects receiving oral rescue corticosteroid treatment
 
Subjects whose oral rescue corticosteroid treatment is tapered
 
	• response
	• Time to first intake of oral rescue corticosteroid treatment	• time to event
EQ-5D-5L from Baseline to Week 53	
 
Mobility
 
Self-care
 
Usual Activities
 
	• cumulative distribution function
Reduction of oral concomitant corticosteroid treatment from Baseline to Week 53	
 
Subjects who start oral concomitant corticosteroid dose taper before Week 25, ie, there is a reduction in week 24
 
Subjects who are able to reduce the oral concomitant corticosteroid treatment at the end of each period by 
 
≥ 25%
 
≥ 50%
 
≥ 75%
 
 
 
	• response

The following additional analyses will be provided:

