## 10.6 Analysis of Exploratory Endpoints

The exploratory endpoints for Study Period 1 and Study Period 2 listed in Table 12 will be summarized descriptively similarly to secondary efficacy endpoints as described in Section 10.5. No comparison between treatment sequences will be done.

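### The Kolmogorov-Smirnov test on changes in 5-level EQ-5D-5L items has no tie handling specified; with its standard p-value it is severely conservative and can hide moderate effects

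*SAP*

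**What the plan says.** SAP Table 11, in the row "EQ-5D-5L from Baseline to Week 53", lists Mobility, Self-care and Usual Activities and gives the summary type as "cumulative distribution function". The matching part of SAP Section 10.5 has two bullets. The first is descriptive: "Change from reference visit will be summarized using frequency counts of levels of improvements/worsening". The second is the test: "The Kolmogorov-Smirnov test will be used to test the equality of the two distribution functions". Nothing is said about asymptotic, exact or permutation p-values, ties, sidedness, strata or Baseline level. SAP Section 7 names SAS as the software but no procedure or option for this test.

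Each item has five levels; SAP Section 8.2.19 counts the combinations over five items ("A total of 3125 possible health states is defined in this way", which is 5^5). A change in level can therefore take at most nine values.

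On the status of the result, SAP Section 10.5 says "P-values from the statistical models are descriptive". For the other two items, Pain/discomfort and Anxiety/depression, SAP Section 10.6 says "No comparison between treatment sequences will be done", so the test concerns three items only. Protocol Section 10.4.2.4.5 compares the sequences on these items through the cumulative distribution function and names no test.

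**The concern.** The standard Kolmogorov-Smirnov p-value is derived for continuous data. When the data fall on a few integers, with many subjects at zero, the two empirical distribution functions can separate at only a few points. The largest gap is then smaller by chance than the reference distribution allows for, and the test rejects far less often than its nominal level. Power falls with it.

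The other comparative models in SAP Section 10.5 use more of the design: the Cox model includes region and MMT-8 stratum, and the repeated-measures model includes the reference-visit value. This test uses neither.

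At stake is how three patient-reported function items are read in Study Period 1, the only period with a placebo comparison. A large p-value could be taken as evidence of no difference when the test had little chance of finding one.

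**Working it through.** **Inputs from the documents.** 63 per arm (SAP Section 4.5), five levels per item (SAP Section 8.2.19), no imputation for secondary endpoints (SAP Section 10.5), so 63 is an upper limit. The documents give no expected distribution of changes, effect size, alpha or power for this test. Those used below, including two-sided 0.05, are assumptions.

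**The plan's own power figure, to confirm the sample size.** SAP Table 3 implies these responder rates:
- Sequence A: 0.65 × (0.9×0.9 + 0.1×0.2) + 0.35 × 0.2×0.9 = 0.5395 + 0.0630 = 0.6025
- Sequence B: 0.30 × (0.9×0.9 + 0.1×0.1) + 0.70 × 0.1×0.9 = 0.2460 + 0.0630 = 0.3090

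Exact one-sided Fisher power at 63 per arm is 0.904; SAP Table 14 gives 0.905.

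**Gap needed to reject.** The asymptotic p-value depends on D × √(63/2). A gap of 15/63 gives p = 0.056 and 16/63 gives p = 0.034. The test therefore needs an observed gap of 16/63, or 25.4 percentage points.

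**Hand check on one assumed shift.** Five change categories, worst to best: placebo 5/15/50/22/8%, IgPro20 2/10/40/30/18%. Cumulative: 5/20/70/92 against 2/12/52/82. The largest true gap is 70 − 52 = 18 points, below the 25.4 needed. Using 15.5/63 = 0.246 as the continuity-corrected threshold:
- Size, both arms as placebo. At the 70% cut, SD = √(2×0.70×0.30/63) = 0.082, so the threshold is 3.0 SD (two-sided tail about 0.0026). At the 20% cut, SD = √(2×0.20×0.80/63) = 0.071, so it is 3.4 to 3.5 SD (about 0.0006). The other cuts add almost nothing. Total: about 0.003.
- Power, at the main cut. SD = √((0.70×0.30 + 0.52×0.48)/63) = 0.085; (0.246 − 0.18)/0.085 = 0.77; upper tail 0.22.

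Simulation of the same case:

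| Test, 63 per arm | Size | Power |
|---|---|---|
| Standard Kolmogorov-Smirnov | 0.003 | 0.22 |
| Permutation Kolmogorov-Smirnov | 0.034 | 0.47 |
| Tie-corrected Wilcoxon | 0.047 | 0.61 |

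The loss against Wilcoxon is 1 − 0.22/0.61 = 64%.

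**Size under other assumed distributions** (40,000 simulated trials per cell, 63 per arm): 0.0001 with 75% unchanged, 0.0014 with 60%, 0.005 with 40%, 0.009 if uniform over five values, 0.016 if uniform over nine. The exact p-value that ignores ties gives the same decisions.

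**Power with 60% of placebo subjects unchanged**, effect as a common odds ratio (losses computed before rounding):

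| Odds ratio | Standard KS | KS recalibrated to the discrete null | Wilcoxon | Loss, standard KS vs Wilcoxon |
|---|---|---|---|---|
| 1.5 | 0.02 | 0.17 | 0.21 | 90% |
| 2 | 0.12 | 0.45 | 0.52 | 76% |
| 2.5 | 0.31 | 0.70 | 0.76 | 59% |
| 3 | 0.52 | 0.85 | 0.89 | 41% |
| 4 | 0.82 | 0.97 | 0.98 | 16% |

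At odds ratio 2 the loss is 91% with 75% unchanged, 64% with 40%, 54% if uniform over five values and 45% if uniform over nine. At odds ratio 4 it is 34% with 75% unchanged and 10% with 40%. The pattern at 50 per arm is the same.

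**The case against.** **The p-value method is open.** The SAP does not exclude a permutation p-value, and that version recovers much of the loss (0.47 against 0.22 in the hand-checked case). This stands. The fault lies in the unspecified p-value as much as in the choice of test, and stating the method is the smallest repair. It does not remove the point, because a programmer following the text may well report the standard p-value.

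**The consequence is limited.** The p-values are descriptive and lie outside the gatekeeping family in SAP Section 4.2.2. Counts of level changes are tabulated anyway, so a real shift would be visible there. After Week 25 both sequences receive IgPro20, so the placebo comparison concerns Study Period 1 only. All of this stands.

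**The test follows the protocol's wording.** Testing equality of two distribution functions is a natural reading of Protocol Section 10.4.2.4.5, and testing for any difference instead of a shift is a choice, not an error. That also stands, but the protocol names no test and so does not rule out a better one.

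**Stratified replacements could meet sparse cells**, since Protocol Section 3.5 plans for at least 10 Japanese subjects. A van Elteren test simulated over assumed sparse region-by-MMT-8 strata held its size (0.053) and power (0.62), so this objection does not stand.

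**Stronger readings.** A reader might infer that the test always loses more than half the power, or that the comparison is close to uninformative. The documents support neither. They give no effect size or distribution of changes, the loss falls to 10 to 16% at odds ratio 4 with 40 to 60% unchanged, and the level counts are reported whatever the p-value.

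**Conclusion.** The point holds in a limited form. With the standard continuous-null p-value, the planned test has an actual size of about 0.0001 to 0.016 at a nominal 0.05. That is below nominal by a factor of 3 (0.05/0.016) to 500 (0.05/0.0001). The low size needs no assumption about effect and appeared under every distribution tried.

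The power loss does depend on assumptions. It exceeds half for odds ratios up to about 2.5 when 60% are unchanged, and up to about 2 when 40% are unchanged or changes are uniform over five values. It is smaller for large effects.

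No primary or key secondary conclusion is affected and there is no inflation of type I error. The exposure is a misleading descriptive p-value on three secondary items in Study Period 1, which makes this an improvement worth making and not a condition for the trial's validity.

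**What to change.** In SAP Section 10.5, replace the Kolmogorov-Smirnov bullet with one of the following, stating sidedness and tie handling:
- a van Elteren test (stratified, tie-corrected Wilcoxon) by MMT-8 stratum and region; or
- a proportional-odds model for change in level, with Baseline level and the two strata.

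At minimum, keep the Kolmogorov-Smirnov test and specify a permutation p-value calibrated to the tied data. In every case keep the cumulative distribution summaries and the counts of level changes as description.

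The cost is a short SAP edit and a small programming change, with no new data and no alpha. Protocol Section 10.4.2.4.5 names no test, so its wording does not stand in the way. There is a small downside: a rank or ordinal test targets a shift instead of any difference in distribution, and proportional odds adds a model assumption. The permutation option avoids both but recovers less power. The proportional-odds option was not simulated here.

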**Table 11: Secondary Efficacy Endpoints - Variables**

Endpoint	Variable	Type of summary measure
TIS from Week 5 to Week 53	• TIS values	• continuous
	• Subjects achieving TIS $\geq 20$ points per visit • Subjects achieving TIS $\geq 40$ points per visit • Subjects achieving TIS $\geq 60$ points per visit • Subjects achieving TIS $\geq 20$ points at the end of Study Period 2	• response
	• Time to first achieving TIS $\geq 20$ points • Time to first achieving TIS $\geq 40$ points • Time to first achieving TIS $\geq 60$ points	• time to event
CDASI from Baseline to Week 53	• CDASI total activity score  Note: For Study Period 2 changes from baseline will also be calculated	• continuous
CSMs (except muscle enzymes) from Baseline to Week 53	• Physician Global Disease Activity • Patient Global Activity • MMT-8 • HAQ-DI • Extramuscular global activity	• continuous

Endpoint	Variable	Type of summary measure
	Note: For Study Period 2 changes from baseline will also be calculated	
DOW from Baseline to Week 53	
 
Subjects meeting DOW at least once per period
 
Subjects meeting DOW at least twice per period
 
Subjects meeting DOW more than twice per period
 
	• response
	• Time to meet DOW for the first time	• time to event
	• Subjects meeting DOW followed by oral rescue corticosteroid treatment per period	• response
Oral rescue corticosteroid treatment (from Baseline to Week 25)	
 
Subjects receiving oral rescue corticosteroid treatment
 
Subjects whose oral rescue corticosteroid treatment is tapered
 
	• response
	• Time to first intake of oral rescue corticosteroid treatment	• time to event
EQ-5D-5L from Baseline to Week 53	
 
Mobility
 
Self-care
 
Usual Activities
 
	• cumulative distribution function
Reduction of oral concomitant corticosteroid treatment from Baseline to Week 53	
 
Subjects who start oral concomitant corticosteroid dose taper before Week 25, ie, there is a reduction in week 24
 
Subjects who are able to reduce the oral concomitant corticosteroid treatment at the end of each period by 
 
≥ 25%
 
≥ 50%
 
≥ 75%
 
 
 
	• response

The following additional analyses will be provided:

- For the most abnormal muscle enzyme (CSM 5) summarizing analysis will be provided for the absolute percent change from baseline to Week 53 in analogy to the analyses for the other CSMs.

- For subjects with available TIS at Week 25 it will be investigated in how many CSMs improvement was achieved. This analysis will be done by TIS improvement category at Week 25 (TIS  $\geq$  20, TIS  $\geq$  40, TIS  $\geq$  60).
- For subjects with a baseline CDASI Total Activity Score  $> 0$ , the proportion of subjects showing an improvement of more than 35% from baseline will be provided per visit. The corresponding analysis will also be done for the subgroup of patients with
  - baseline CDASI Total Activity Score  $\leq 14$  and  $> 0$
  - baseline CDASI Total Activity Score  $> 14$

## 10.6 Analysis of Exploratory Endpoints

The exploratory endpoints for Study Period 1 and Study Period 2 listed in Table 12 will be summarized descriptively similarly to secondary efficacy endpoints as described in Section 10.5. No comparison between treatment sequences will be done.

**Table 12: Exploratory Endpoints – Variables (Study Period 1 and Study Period 2)**

Endpoint	Variable	Type of summary measure
EQ-5D-5L	
 
• Pain/ discomfort
 
• Anxiety/ depression
 
	
 
• cumulative distribution function
 

	
 
• Utility index
 
• Health VAS
 
	
 
• continuous
 

WPAI-GH	
 
• Percent work time missed due to health
 
• Percent impairment while working due to health
 
• Percent overall work impairment due to health
 
• Percent activity impairment due to health
 
	
 
• continuous
 

TSQM-9	
 
• Effectiveness
 
• Convenience
 
• Global Satisfaction
 
• Item 1 to Item 9
 
 
Change from Baseline will not be summarized as there is no Baseline assessment for TSQM-9.
	
 
• continuous
 

Endpoint	Variable	Type of summary measure
Timed Up and Go	• Timed Up and Go	• categorical (see Section 8.2.29)
5-D Itch score	• Total score	• continuous
Muscle enzymes	Serum levels of • CK (IU/L) • LDH (IU/L) • AST (IU/L) • ALT (IU/L) • aldolase (IU/L)	• continuous
Serum IgG	• IgG serum concentrations	• continuous
	• IgG PK parameters $C_{max}$ , $C_{trough}$ , and AUC	• see Section 12
IIM autoimmune antibody panel	• MSA • MAA • ANA	• Response, categorical, continuous
HAQ	• Pain VAS	• continuous
MDAAT	• VAS Constitutional Disease Activity • VAS Cutaneous Disease Activity • VAS Skeletal Disease Activity • VAS Gastrointestinal Disease Activity • VAS Pulmonary Disease Activity • VAS Cardiovascular Disease Activity • VAS Other Disease Activity	• continuous
CDASI	• Total score • Total damage score	• continuous
Reduction of oral concomitant corticosteroid treatment	• Percent reduction of average daily dose	• continuous

The exploratory endpoints listed in Table 13 for Study Period 3 will be summarized descriptively only as described in Section 10.5. The data will be presented by sequence and overall including

visits from all 3 study periods based on the SAF-P3. Reference visits are described in Section 8.2.1.

**Table 13: Exploratory Endpoints – Variables (Study Period 3)**

Endpoint	Variable	Type of summary measure
CSMs	
 
• Physician Global Disease Activity
 
• Patient Global Activity
 
• MMT-8
 
• HAQ-DI
 
	• continuous
HAQ	
 
• Pain VAS
 
	• continuous
CDASI	
 
• Total activity score
 
• Total score
 
• Total damage score
 
	• continuous
EQ-5D-5L	
 
• Mobility
 
• Self-care
 
• Usual Activities
 
• Pain/ discomfort
 
• Anxiety/ depression
 
	• cumulative distribution function
	
 
• Utility index
 
• Health VAS
 
	• continuous
Corticosteroid treatment	
 
• Percent reduction of average daily dose
 
	• continuous

## 10.7 Treatment Compliance

Treatment compliance will be summarized for each period, by treatment sequence using descriptive statistics. The number and percentage of subjects who are compliant or non-compliant will be presented for each period.

Weekly treatment compliance with assigned IMP is determined using the algorithm:

$$\text{compliance (\%)} = (\text{actual volume infused}/\text{planned volume}) \times 100.$$

A subject will be considered to be compliant with the assigned IMP for the week if the weekly compliance is between 80% and 120%. If a subject's weekly compliance is less than 80% or greater than 120%, he/she will be considered to be non-compliant with the assigned IMP for that week.

For the duration of each period of a subject overall, the subject will be considered to be compliant with the assigned IMP if he/she is compliant for at least 80% of his/her duration of that period. If the subject is non-compliant at more than 20% of his/her duration, then he/she will be considered to be non-compliant with the assigned IMP for that period.

## 11 Safety Analyses

All Safety analyses will be performed for the following periods and analysis sets:

- Week 1-EOP1 by treatment sequence (SAF)
- Week 25-EOP2 by treatment sequence (SAF-Ex)
- Week 53-EOP3 by treatment sequence (SAF-P3)

Additionally, adverse events will be presented using the following periods and analysis sets:

- IgPro20 Periods (SAF-IgPro20)  
Note: This is restricted to IgPro20 treatment

### 11.1 Extent of Exposure

Exposure to the investigational product will be descriptively summarized by period and treatment sequence:

- Duration of exposure (days) per subject\*
- Number of infusions (partial or complete) administered per subject\*
- Number of days with infusions per subject\*
- Total dose received (g) per subject\*
- Total volume received (mL) per subject\*
- Maximum volume per infusion site (mL) (categorized) per days with infusions\*
- Maximum volume per infusion site (mL) (continuous) per weeks with infusions, per days with infusions, and per infusion
- Maximum infusion rate per infusion site (mL/h) (categorized) per days with infusions\*
- Maximum infusion rate per infusion site (mL/h) (continuous) per weeks with infusions, per days with infusions, and per infusion
- Actual total volume (mL) per weeks with infusions, per days with infusions, and per infusion

- Actual total dose (g/kg body weight) per weeks with infusions
- Duration of infusion (minutes) per weeks with infusions, per days with infusions, and per infusion
- Number of infusion sites per infusion
- Overall compliance per subject\*
- Percentage of subjects requiring additional infusion training in Week 3 or Week 4

Analyses marked with \* will also be provided for the subgroup of Japanese subjects.

Following data will be summarized for each week by treatment sequence:

- Actual total volume (mL) per subject
- Actual total dose (g/kg body weight) per subject
- Maximum volume per infusion site (mL) per subject
- Maximum infusion rate per infusion site (mL/h) per subject
- Duration of infusion (minutes) per subject

The listing of individual subject data will include all variables presented in the summary tables.

